### **6.2 Appendix 2: Disposition of study participants**

Study participant disposition will be listed for the ASPS and will include the following information: study participant status (screen failure, completed or discontinued), date of informed consent, date of IMP administration, and date of premature study and/or study drug termination (if applicable).

Study participant disposition will be summarized for the ASPS. The disposition table will include the reasons for screen failure, the number of study participants starting the Sampling

Period, the number of study participants completing the study, and reasons for discontinuation of study.

The study participants included in each of the analysis sets will be listed and summarized for the ASPS.

### 6.3 Appendix 3: Baseline characteristics and demographics

A listing of demographics by study participant will be presented for the ASPS. This will include the year of birth, age (in years), race, ethnicity, height (cm), weight at Screening and Day 1 predose (kg), body mass index (BMI, in kg/m^2 to 1 decimal place) at Screening and Day 1 predose, and time postpartum on Day 1.

All demographic characteristics taken at Screening (except for year of birth) will be summarized for the ASPS. The summary of age will include descriptive statistics and categorical summaries, the latter based on requirements for European Union Drug Regulating Authorities Clinical Trials (EudraCT) reporting.

For the EudraCT reporting, the categories will include:

- 18 to <65 years
- 65 to <85 years
- ≥85 years

BMI in kg/m^2 is calculated based on the height (in m) at Screening and the weight at Screening or Day 1 predose (in kg) using the following formula (if height is in cm, then height will be converted to meters by dividing by 100):

$$BMI (kg/m^2) = weight (kg) / [height (m)]^2$$

The BMI will be derived and automatically reported to 1 decimal place on the eCRF.

### 6.4 Appendix 4: Protocol deviations

All protocol deviations will be reviewed at the Data Cleaning Meetings (DCM) and decisions made on whether they should be considered important or not.

Important protocol deviations (IPDs) are deviations from the protocol which could potentially have a meaningful impact on study conduct or on either the primary or secondary outcome(s) for an individual study participant. The criteria for identifying such protocol deviations will be defined within the PD specifications document.

All protocol deviations will be categorized as follows:

- Inclusion/exclusion criteria deviations
- Incorrect treatment or dose administered
- Procedural non-compliance
- Prohibited concomitant medication use
- Withdrawal criteria deviation
- Other

Should a participant be mistakenly dosed despite failing the inclusion/exclusion criteria, then their safety data would need to be reported as part of the safety analysis. Participants may be excluded from other analysis sets, but this will be determined on a case-by-case basis. If the deviation is deemed to have the potential to bias the analyses for the duration of the study, then the whole participant may be removed in a sensitivity analysis on the key endpoints. The removal of the participant and the rationale will be clearly documented within the relevant TFLs.

Important protocol deviations will be identified and classified by the deviation types. A listing of all IPDs will be presented for all participants in the safety set and will include the deviation type and description.

The IPDs will be tabulated using the SS and will present the deviation type and description.

## 6.5 Appendix 5: Medical history

Medical history and ongoing medical conditions will be summarized for the SS by system organ class (SOC) and preferred term (PT). The summary will include the number and percentage of study participants and will be sorted alphabetically by SOC and by descending incidence of PT within each SOC.

## 6.6 Appendix 6: Past/prior/concomitant medications

For the purposes of this study:

- **Past medications** include those that started and stopped prior to administration of the study drug.
- **Prior medications** include those that started prior to administration of the study drug and either stopped prior to administration of the study drug or continued after administration of the study drug.
- **Baseline medications** include those that started prior to administration of the study drug and continued after administration of the study drug.
- **Newly concomitant medications** include those that started any time between administration of the study drug until the SFU Visit.
- **Concomitant medications** include both baseline and newly concomitant medications, being those that have been taken at least once between the administration of the study drug and the SFU Visit.

Past, baseline (includes prior/concomitant) and newly concomitant medications will be summarized based on the SS. These classifications of medications will be summarized in separate tables. The tables will be sorted alphabetically by Level 1 term, alphabetical Level 3 term within Level 1 and decreasing frequency of PT.

Past, baseline (includes prior/concomitant), and newly concomitant medications will be listed for the SS.

## 6.7 Appendix 7: AEs of special interest/special monitoring

Adverse events of special interest and AEs of special monitoring will be listed for the ASPs. If there are any events, AESIs and AESMs will be summarized for the SS.

### 6.7.1 AEs of Special Interest

Potential Hy's Law is defined as  $\geq 3$ x upper limit of normal (ULN) alanine aminotransferase (ALT) or aspartate aminotransferase (AST) with coexisting  $\geq 2$ xULN total bilirubin in the absence of  $\geq 2$ xULN alkaline phosphate (ALP), with no alternative explanation for the biochemical abnormality (i.e., without waiting for any additional etiologic investigations to have been concluded). AESIs will be identified via the AE form in the eCRF.

### 6.7.2 AEs of Special Monitoring

For rozanolixizumab, the following events are AESM that require immediate reporting (within 24 hours regardless of seriousness) to UCB:

- Severe and/or serious headache
- Suspected aseptic meningitis

AESMs will be identified via the AE form in the eCRF.

## 6.8 Appendix 8: AEs of focus

The following events are adverse events of focus for rozanolixizumab for all indications unless otherwise noted. Adverse events of focus will be listed for the ASPs. If there are any events, AEs of focus will be summarized for the SS.

**Table 6–1: AEs of focus**

Number	Event	Selection criteria
1	Headache	TEAE with HLGT='Headaches'
2	Possible aseptic meningitis	SMQ=' Noninfectious meningitis' narrow search

**Table 6–1: AEs of focus**

Number	Event	Selection criteria
3	Gastrointestinal disturbances	TEAE with HLT= ‘Gastrointestinal and abdominal pains (excl oral and throat)’ or HLT= ‘Nausea and vomiting symptoms’ or HLT= ‘Diarrhoea (excl infective)’ or HLT= ‘Gastritis (excl infective)’ or PT= ‘Abdominal discomfort’
4	Hypersensitivity reactions	SMQ = ‘Hypersensitivity’ narrow search
5	Anaphylactic reactions	
SMQ = ‘Anaphylactic reaction’ and TEAEs that either emerged on the same day as when a study medication injection reaction was received, or that emerged one day after a study medication injection was received, and which fulfill any of the following 3 criteria should be included in the summary table:
 
 
1. If a subject reports any TEAE which codes to a PT included in Category A, then the event will be flagged as an anaphylactic reaction.
 
2. If a subject reports any TEAE which codes to a PT included in Category B AND reports any TEAE which codes to a PT included in Category C, and both TEAEs have the same start date, then both events will be flagged as anaphylactic reactions.
 
3. If a subject reports any TEAE which codes to a PT included in Category D AND reports (either a TEAE which codes to a PT included in Category B OR a TEAE which codes to a PT included in Category
 

**Table 6–1: AEs of focus**

Number	Event	Selection criteria
		C), and both TEAEs have the same start date, then both events will be flagged as anaphylactic reactions.
6	Injection site reactions	TEAE with HLT='Injection site reactions' or HLT='Infusion site reactions' or HLT='Administration site reactions NEC'
7	Infections	TEAE with SOC = "Infections and infestations" Note: This was added as a reminder for safety that infections are considered as AE of focus and require assessment. No programming of this topic is required as TEAEs can be found in general AE Tables.
8	Opportunistic infections (Note: also included in AESM)	TEAEs in MedDRA SMQ = 'Opportunistic infections' narrow search
9	Reductions in albumin and plasma proteins (N/A in DB studies where values are blinded)	TEAEs with PT='Blood albumin decreased' or PT='Protein albumin ratio' or LLT='Plasma protein abnormal' or LLT='Proteins serum plasma low'
10	Effects on the kidney	TEAEs in SMQ= 'Acute renal failure' narrow search

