## Recording and follow up of AE and/or SAE

### AE and SAE recording

- When an AE/SAE occurs, it is the responsibility of the investigator to review all documentation (eg, hospital progress notes, laboratory reports, and diagnostics reports) related to the event.
- The investigator will then record all relevant AE/SAE information in the CRF.
- It is **not** acceptable for the investigator to send photocopies of the study participant's medical records to UCB in lieu of completion of the UCB AE/SAE CRF page.
- There may be instances when copies of medical records for certain cases are requested by UCB. In this case, all study participant identifiers, with the exception of the participant number, will be redacted on the copies of the medical records before submission to UCB.
- The investigator will attempt to establish a diagnosis of the event based on signs, symptoms, and/or other clinical information. Whenever possible, the diagnosis (not the individual signs/symptoms) will be documented as the AE/SAE.

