##### **4.3.1.2 Main analytical approach**

The number and percentage of participants who experience TEAEs will be summarized by MedDRA SOC, HLT, and PT. Summaries of TEAEs include, but are not limited to the following:

- Incidence of overall TEAEs (overview including number and percentage of participants with any TEAEs, serious TEAEs, discontinuations due to TEAEs, drug-related TEAEs, severe TEAEs, TEAEs leading to death, all deaths, TEAEs of Special Interest (Hy's Law), TEAEs of Special Monitoring, TEAEs of focus, ADEs, severe ADEs, and SAEs; event counts will also be included)
- Incidence of all TEAEs
- Incidence of Serious TEAEs
- Incidence of TEAEs by maximum intensity
- Incidence of TEAEs by maximum relationship
- Incidence of non-serious TEAEs above reporting threshold of 5% of study participants
- Incidence of all TEAEs by Preferred Term
- Discontinuation due to AEs
- Incidence of Serious TEAEs by Relationship
- Incidence of Fatal TEAEs by Relationship

Summary tables will contain counts of study participants, percentages of study participants in parentheses and the number of events where applicable. A participant who has multiple events in the same SOC, HLT, and PT during a given treatment will be counted only once in the participant counts for that treatment, but all events will be included.

Rozanolixizumab treatment-emergent adverse events of focus (TEAEOF) will also be analysed for the SS. TEAEOF are defined in Section 6.8. The number of and percentage of study participants who experience each category of the TEAEOF will be summarized. The following summaries will be presented by SOC, HLT and PT:

- Incidence of TEAEOF
- Incidence of Serious TEAEOF

In summaries including relationship, the following relationships will be summarized: 'Not related' and 'Related'. Participants who experience the same event multiple times will be included in the most related category for tabulations by maximum relationship. Events with missing relationship will be considered as 'Related' but recorded as missing in the listings.

In summaries including intensity, the following intensity categories will be summarized: 'Any', 'Mild', 'Moderate', and 'Severe'. Participants who experience the same event multiple times will be included in the most severe category for tabulations by maximum intensity. Events with missing intensity will be considered as 'Severe' events for summary purposes but recorded as missing in the listings.

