**Table 6–1: AEs of focus**

Number	Event	Selection criteria
11	Drug related hepatic disorders	TEAEs in SMQ='Drug related hepatic disorders - comprehensive search' narrow and broad search
12	Effect on lipids	TEAEs with PT= 'Blood cholesterol increased' or PT= 'Low density lipoprotein increased' or PT= 'Blood triglycerides increased' or PT= 'Hypercholesterolaemia' or PT= 'Hypertriglyceridaemia' or PT= 'Hyperlipidaemia' or PT= 'Dyslipidaemia' or PT= 'Lipids increased'

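### The AE-of-focus rule for reductions in albumin and plasma proteins names no diagnosis term, and two of its four terms state no direction, so its count can be wrong (minor)

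*SAP*

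**What the plan says.** SAP Section 6.8, Table 6-1, row 9 is labelled "Reductions in albumin and plasma proteins (N/A in DB studies where values are blinded"). Its selection rule starts with the preferred term *Blood albumin decreased* and continues "PT='Protein albumin ratio' or LLT='Plasma protein abnormal' or LLT='Proteins serum plasma low". It has no high-level term and no standardised query that would bring in related terms.

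Row 12, on lipids, begins "PT= 'Blood cholesterol increased' or PT= 'Low density lipoprotein increased' or PT= 'Blood triglycerides increased" and continues "PT= 'Hypercholesterolaemia' or PT= 'Hypertriglyceridaemia' or PT= 'Hyperlipidaemia' or PT= 'Dyslipidaemia' or PT= 'Lipids increased".

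SAP Section 4.3.1.2 commits to a result for each category: "The number of and percentage of study participants who experience each category of the TEAEOF will be summarized". SAP Section 6.8 adds a listing.

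On how events reach the database, Protocol Appendix 3 (AE and SAE recording) says: "Whenever possible, the diagnosis (not the individual signs/symptoms) will be documented as the AE/SAE". SAP Section 6.1 fixes the dictionary as MedDRA 27.1.

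**The concern.** An AE-of-focus category is useful only if its selection rule captures the event that its label names. Row 9 is a closed list, so a term that is not named is not selected. If the same low albumin can be written either as a laboratory result or as a diagnosis, and only the first is on the list, the count depends on the investigator's choice of wording. The protocol's recording instruction leans towards the wording that is not on the list.

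The two terms without direction create the opposite risk: an event that is not a fall could be counted under a label that says reductions.

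At stake is one line of a supplementary safety summary. A reader who sees few or no participants there could conclude that albumin and protein reductions were not reported as adverse events when some were.

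**Working it through.** The plan gives no figure to reproduce. The check classifies the listed terms and compares the two rows.

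**Step 1: classify the terms by their wording.**

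| | Row 9 (albumin, proteins) | Row 12 (lipids) |
|---|---|---|
| Terms listed | 4 | 8 |
| Worded as a laboratory result | 4 | 4 |
| Worded as a diagnosis | 0 | 4 |
| Laboratory terms with no direction | 2 | 0 |
| Row label | directional (reductions) | neutral (effect on lipids) |

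The four diagnoses in row 12 are *Hypercholesterolaemia*, *Hypertriglyceridaemia*, *Hyperlipidaemia* and *Dyslipidaemia*. The two terms without direction in row 9 are *Protein albumin ratio* and *Plasma protein abnormal*.

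**Step 2: does a diagnosis have to be named to be selected?** Row 12 names *Hypercholesterolaemia* as well as *Blood cholesterol increased*, and *Hypertriglyceridaemia* as well as *Blood triglycerides increased*. For lipids, then, the table treats the diagnosis as a separate preferred term that the rule must list. If albumin and protein work the same way, an event entered as hypoalbuminaemia or hypoproteinaemia falls outside row 9. The dictionary is not reproduced in the documents, so this step is an assumption supported by analogy.

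**Step 3: does the direction problem need the dictionary?** No. The label says reductions, and two listed terms carry no such condition. *Dyslipidaemia* in row 12 also states no direction, but that row's label is neutral, so it does not conflict with its label.

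**Step 4: do other outputs cover the gap?** In part.
- The general TEAE tables (SAP Section 4.3.1.2) show every event by SOC, HLT and PT. Row 7 says expressly that infections need no separate programming because the general tables suffice. Row 9 carries no such note, so its category is meant to be programmed.
- Chemistry is summarised by visit, but scheduled laboratory tests fall at Screening, Day 1 predose and Visit 4 only (Protocol Table 1-1); Visit 4 is Day 3 (SAP Table 4-1). TEAEs are counted for 56 days (SAP Section 4.3.1.1). A fall found later would come from an unscheduled test, which SAP Section 4.1.1.4 places in listings.
- The marked-abnormality analysis is optional (SAP Section 4.5.2). Its albumin limit is below 20 g/L, and SAP Table 6-4 has no total-protein limit, although total protein is measured (Protocol Appendix 2).

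**Step 5: scale.** The shift in category incidence from one misclassified participant is 1/N. With the planned 12 to 15 women providing data, 1/15 = 6.7% and 1/12 = 8.3%. The Safety Set may be larger, because women who withdraw before Day 7 may be replaced (Protocol Section 7.2). If all 20 planned for screening were dosed, 1/20 = 5.0%. This is the weight of one woman, not an estimate of how many would be misclassified.

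**The case against.** The strongest reply is that nothing is lost to the study. The secondary safety endpoint is the occurrence of TEAEs, every TEAE is tabulated and every AE is listed. Albumin and total protein are measured, chemistry is summarised, and out-of-range results are listed. In healthy women given one dose, with one scheduled chemistry draw afterwards, such events may be rare. All of this stands, and it is why the point is minor.

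Four stronger readings are tempting, and the documents do not support them.

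- *That hypoalbuminaemia is certainly missed.* This depends on MedDRA 27.1. Row 12 makes it likely but does not prove it for albumin.
- *That a diagnosis is the usual way such an event would be reported.* Protocol Section 8.2.5 and Appendix 3 also treat a clinically significant laboratory abnormality as an AE in its own right. An investigator following that route could well enter a wording that row 9 selects. The documents do not show which wording will predominate.
- *That a fall in plasma protein can enter by one term only.* *Plasma protein abnormal* is a second route.
- *That the two non-directional terms are errors to delete.* A broad term in a safety search may be chosen for sensitivity, and deletion could lose real falls that were reported vaguely. What remains is a mismatch with the row's label, which a check of direction resolves.

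Table 6-1 also reads as a list shared across the rozanolixizumab programme: Section 6.8 says that it applies to all indications unless noted, and row 9 carries a remark about double-blind studies. Changing one row here makes a small departure from that list.

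**Conclusion.** The point holds as a minor one. Row 9 selects by four laboratory-worded terms and no diagnosis, so the category count and listing can be falsely low when a low albumin or protein is entered as a diagnosis. This assumes that MedDRA 27.1 holds the diagnosis under a preferred term of its own. Separately, and without any assumption about the dictionary, two of the four terms do not carry the direction that the label states, so the count could also include an event that is not a reduction.

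The documents give no basis for estimating how often either would happen. The effect stops at the AE-of-focus summary and listing.

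**What to change.** Before database lock, check row 9 against MedDRA 27.1 and revise it as follows:

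- Keep *Blood albumin decreased* and *Proteins serum plasma low*.
- Add the diagnosis terms for hypoalbuminaemia and hypoproteinaemia, and a directional term for decreased total protein, using the exact names in MedDRA 27.1.
- Keep *Protein albumin ratio* and *Plasma protein abnormal*, but count an event coded to either only when the reported verbatim or the participant's laboratory value shows a decrease.

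The cost is one table row, its programming and a short review of any events coded to the two non-directional terms. No new data are needed. The downside is the small departure from what appears to be a programme-wide list; a footnote naming the added terms would let readers compare across studies.

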**Table 6–1: AEs of focus**

Number	Event	Selection criteria
11	Drug related hepatic disorders	TEAEs in SMQ='Drug related hepatic disorders - comprehensive search' narrow and broad search
12	Effect on lipids	TEAEs with PT= 'Blood cholesterol increased' or PT= 'Low density lipoprotein increased' or PT= 'Blood triglycerides increased' or PT= 'Hypercholesterolaemia' or PT= 'Hypertriglyceridaemia' or PT= 'Hyperlipidaemia' or PT= 'Dyslipidaemia' or PT= 'Lipids increased'

## 6.9 Appendix 9: PK calculations

If calculable, pharmacokinetic parameters will be calculated by non-compartmental analysis methods from the concentration-time data following these guidelines:

- Actual time will be used in the calculation of all derived pharmacokinetic parameters.
- There will be no imputation of missing data.
- BLQ values at the beginning of a study participant profile (i.e., before the first incidence of a measurable concentration) will be assigned to zero. Embedded BLQ values (i.e., occurring between two measurable data points) and BLQ values occurring post- $C_{max}$  will be considered missing.

Pharmacokinetic parameters will be estimated according to the guidelines presented in [Table 6–2](#) below.

**Table 6–2: Pharmacokinetic Parameters and Estimation**

Parameter	Guideline for Derivation
$C_{max}$ , $t_{max}$	Obtained directly from the observed concentration-time data. Calculate for rozanolixizumab in breast milk and plasma
$Ae_{7d}$	Cumulative total amount excreted in milk to Day 7

**Table 6–2: Pharmacokinetic Parameters and Estimation**

Parameter	Guideline for Derivation
AUC (0-7d)	The AUC from zero time (pre-dose) to 144 h post dose will be calculated by a combination of the linear and logarithmic trapezoidal methods. Unless specifically requested and justified the linear up/log down trapezoidal method will be employed. Calculate for rozanolixizumab in breast milk and plasma.
Fe	$Ae_{7d}/\text{administered dose (mg)} \times 100 (\%)$
Milk:plasma AUC (0-7d) ratio	$AUC_{(0-7d)} \text{ in breast milk} / AUC_{(0-7d)} \text{ in maternal plasma} \times 100 (\%)$
Relative Infant Dose	$[(\text{Estimated}) \text{ Daily Infant Dosage (mg/kg/day)} / \text{Maternal Dosage (mg/kg/day)}] \times 100 (\%)$ (see Section 4.2.1.1 for details on the calculation of the estimated daily infant dosage)

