#### Estimated daily infant dosage from breastmilk

The estimated daily infant dosage of rozanolixizumab from breast milk will be calculated based on the concentration of rozanolixizumab in mature human breast milk for the PKs.

The amount of rozanolixizumab that the infant may consume following single rozanolixizumab dosing to the mother will be calculated as follows:

$$1. \text{ Estimated daily infant dosage (mg/kg/day)} = \text{M/P ratio} \times C_{\text{av,plasma}} \times 150\text{mL/kg/day}$$

Where M/P ratio is the milk:plasma ratio based on  $\text{AUC}_{(0-7\text{d})}$  and  $C_{\text{av,plasma}}$  is the average maternal plasma concentration calculated as  $\text{AUC}_{(0-7\text{d}),\text{plasma}}/7 \text{ days}$ .

This is based on the standardized mean milk consumption for a fully breastfed 2-month old infant of 150mL/kg/day.

$$2. \text{ Daily infant dosage (mg/day)} = \sum (\text{total drug concentration in each breast milk collection} \times \text{the expressed milk volume (ml) in each collection}) \text{ for each 24hour period of the 7 days postdose.}$$

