#### Relative infant dose from breast milk

The relative infant dose of rozanolixizumab from breast milk will be calculated as follows:

$$\text{Estimated daily infant dosage (mg/kg/day)} / \text{maternal rozanolixizumab dosage (mg/kg/day)} \times 100$$

Where

maternal rozanolixizumab dosage (mg/kg/day)=Actual dose administered/(Day 1 weight\*7)

Plasma PK endpoints will be computed using actual blood sampling time points.

The following exploratory PK parameters will be derived for rozanolixizumab in breast milk:

- $C_{max}$ ,  $t_{max}$ ,  $AUC_{(0-7d)}$
- $Ae_{7d}$  (mg)=cumulative total amount excreted in milk to Day 7
- $Fe=Ae_{7d}/\text{administered dose (mg)} \times 100\%$
- Milk:plasma  $AUC_{(0-7d)}$  ratio

The following exploratory PK parameters will be derived for rozanolixizumab in plasma:

- $C_{max}$ ,  $t_{max}$ ,  $AUC_{(0-7d)}$

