#### **4.8 Changes to protocol-planned analyses**

The definitions of past, prior, and concomitant medications have changed from the protocol and are documented in Section 6.6.

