### **5 SAMPLE SIZE DETERMINATION**

No formal sample size calculations have been performed as there are no statistical hypotheses being tested. It is expected that up to 20 healthy study participants will need to be screened to ensure that a minimum of 12 participants and a maximum of 15 participants provide data to assess whether there is transfer of rozanolixizumab into breast milk after a single dose and to calculate the estimated daily infant dosage and relative infant dose from breast milk. This number was selected based on feasibility and considered to be sufficient to meet the primary objective.

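### SAP Table 6-2 puts the milk:plasma AUC ratio on a percent scale, but the infant dosage formula in SAP 4.2.1.1 needs it as a plain fraction

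*SAP*

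**What the plan says.** The SAP describes this ratio in three places.

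- **SAP 6.9 (Appendix 9)** makes Table 6-2 the rule for PK parameters: "Pharmacokinetic parameters will be estimated according to the guidelines presented in" that table. Its row for the milk:plasma ratio reads AUC(0-7d) "in breast milk} / AUC_{(0-7d)} \text{ in maternal plasma} \times 100", with a percent sign after it. This is the only explicit formula for the ratio in either document.
- **SAP 4.2.1.1, estimated daily infant dosage**, gives the dosage in mg/kg/day as "M/P ratio} \times C_{\text{av,plasma}} \times 150\text{mL/kg/day". The ratio is explained there as follows: "Where M/P ratio is the milk:plasma ratio based on" AUC(0-7d). Average plasma concentration is plasma AUC(0-7d) divided by 7 days. Nothing is divided by 100. Protocol 9.3.1.1 has the same formula.
- **SAP 4.2.1.1, exploratory parameter list**, names the ratio with no factor of 100, although Fe in the same list carries one. Protocol 8.6 and 9.3.2 do the same.

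The relative infant dose takes the mg/kg/day dosage as its numerator and applies its own factor of 100. Its Table 6-2 row refers back to Section 4.2.1.1 "for details on the calculation of the estimated daily infant dosage". Its denominator is "maternal rozanolixizumab dosage (mg/kg/day)=Actual dose administered" divided by Day 1 weight times 7.

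**The concern.** The ratio in Table 6-2 and the M/P ratio in the dosage formula are evidently the same quantity, but the table puts it on a percent scale and the formula needs a fraction. Someone who derives the parameters from Table 6-2 and then passes the stored number into the 4.2.1.1 formula gets the wrong answer while following both texts.

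The two results exposed are the estimated daily infant dosage and the relative infant dose. They are the secondary PK endpoints under the primary objective, and protocol 2.1 names them as the information the study is meant to give breastfeeding women and their physicians. The relative infant dose is properly a percentage, so its percent label would not show that a second factor of 100 had entered.

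**Working it through.** The documents give no value for either AUC, the ratio, the dosage or the relative infant dose (RID), so there is no plan figure to reproduce. The factor follows from algebra. The absolute values below are illustrations on assumed inputs.

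**1. What the formula must equal.** With R = AUC_milk / AUC_plasma and C_av = AUC_plasma / 7,

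R × C_av × 150 = (AUC_milk / AUC_plasma) × (AUC_plasma / 7) × 150 = (AUC_milk / 7) × 150.

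This is average milk concentration times daily intake per kg, the intended quantity. The plasma AUC cancels only if R is the plain fraction.

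**2. With the Table 6-2 number.** Replacing R by 100R gives 100 × (AUC_milk / 7) × 150. The dosage is 100 times the intended value whatever the AUCs.

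**3. Relative infant dose.** RID = dosage / [dose / (weight × 7)] × 100. The denominator does not contain R, so RID carries the same factor of 100 whatever the dose or weight.

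**4. One case in full.** Assume AUC_plasma = 200 µg·day/mL, R = 0.01, dose 560 mg and weight 70 kg.

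- C_av = 200 / 7 = 28.57 µg/mL.
- Maternal dosage = 560 / (70 × 7) = 1.143 mg/kg/day.
- R entered as 0.01: 0.01 × 28.57 × 150 = 42.9 µg/kg/day = 0.0429 mg/kg/day; RID = 0.0429 / 1.143 × 100 = 3.75%.
- Table 6-2 number entered as 1: 1 × 28.57 × 150 = 4286 µg/kg/day = 4.29 mg/kg/day; RID = 375%.
- Table 6-2 value read as 1%: 1% is 0.01, so the result is again 0.0429 mg/kg/day and 3.75%.

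**5. Range over assumed inputs (560 mg, 70 kg).**

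| AUC_plasma (µg·day/mL) | R | Dosage, fraction (mg/kg/day) | Dosage, bare Table 6-2 number | RID, fraction | RID, bare Table 6-2 number |
|---|---|---|---|---|---|
| 50 | 0.001 | 0.00107 | 0.107 | 0.094% | 9.38% |
| 50 | 0.01 | 0.0107 | 1.07 | 0.94% | 93.8% |
| 50 | 0.1 | 0.107 | 10.7 | 9.38% | 938% |
| 200 | 0.001 | 0.00429 | 0.429 | 0.375% | 37.5% |
| 200 | 0.01 | 0.0429 | 4.29 | 3.75% | 375% |
| 200 | 0.1 | 0.429 | 42.9 | 37.5% | 3750% |

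Adding 420 mg at 45 kg and 840 mg at 110 kg makes 18 combinations. The factor is 100 in all of them.

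**6. Would it be noticed?** The inflated RID passes 100% only when the true RID exceeds 1%. Below that, as in the rows giving 9.38%, 37.5% and 93.8%, the wrong value is not impossible on its face.

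**7. What does not use the ratio.** Milk concentrations (the primary endpoint), Ae7d, Fe and the second infant dosage in SAP 4.2.1.1 (mg/day, from concentration times expressed volume) are unaffected.

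**The case against.** A reader might infer that the SAP as written prescribes a dosage and RID 100 times too high. The documents do not support that, for two reasons. First, the Table 6-2 rule ends in a percent sign; 0.5% is 0.005, and with that value the 4.2.1.1 formula is correct. Second, 4.2.1.1 describes its own input as a ratio based on the AUCs, does not point to Table 6-2, and lists the ratio without a factor of 100 beside Fe, which has one. The cross-reference runs the other way, from the RID row of Table 6-2 to 4.2.1.1. Both arguments stand, so the error is conditional.

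A reader might also infer that the SAP departs from a protocol formula without saying so, since SAP 4.8 declares only this: "The definitions of past, prior, and concomitant medications have changed from the protocol and are documented in Section 6.6". That is also too strong. Protocol 8.6 and 9.3.2 name the ratio but give no formula, and reporting an exploratory ratio as a percentage is legitimate. The contrast with Fe suggests a plain ratio was meant, no more.

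There are also safeguards. Milk AUC is to be listed, so the dosage can be recomputed from it. The mg/day dosage gives an independent order-of-magnitude check. At moderate transfer an inflated RID would exceed 100% and draw attention. These lower the risk without removing it: the SAP specifies no such cross-check, and at low transfer the wrong RID could pass.

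What remains is that SAP 6.9 makes Table 6-2 the guideline for PK parameters, and its stated number does not fit the formula that uses the same parameter.

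**Conclusion.** The point holds as an inconsistency between two definitions in the SAP. If the Table 6-2 value is carried into the dosage formula as a bare number, the estimated daily infant dosage and the relative infant dose are each exactly 100 times too high. If it is read as a percentage, or the unscaled ratio is used, both are right. The documents do not settle which would happen, so the factor of 100 is the size of one possible implementation and not a prediction.

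The factor needs no assumption about AUC, dose or weight; every absolute figure above rests on assumed AUCs, ratios and weights. The effect is confined to the two secondary PK endpoints of a descriptive study. It should be corrected before the PK parameters are programmed, but it does not invalidate the plan.

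**What to change.** Make one of these changes in the SAP:

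- delete the factor of 100 and the percent sign from the milk:plasma ratio row of Table 6-2; or
- keep the percentage for display only, and state in 4.2.1.1 that M/P enters as the unscaled fraction AUC_milk / AUC_plasma.

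Under either change, it helps to add that the estimated daily infant dosage must equal (AUC_milk(0-7d) / 7 days) × 150 mL/kg/day, apart from the conversion to mg. This gives the programmer a direct check.

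The cost is one line of SAP wording. Data collection, analysis sets and the other parameters do not change.
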